- To assess immunologic predictors of virologic response (all subjects) and relapse (among subjects with confirmed AdV clearance from plasma)
- To evaluate exploratory biomarkers for BCV-related gastrointestinal (GI) toxicity (e.g., citrulline, suppression of tumorigenicity-2 [ST2], T cell immunoglobulin mucin-3 [TIM3], and C-reactive protein [CRP])
- To assess healthcare resource utilization

Methodology: This is a randomized, open-label, multi-center study of the safety, overall tolerability, and antiviral activity of BCV, as compared with SoC, in pediatric recipients of high-risk (i.e., T cell-depleted) allogeneic HCT. Pediatric patients with AdV detected in plasma within the previous 21 days and for the first time since their qualifying transplant may be screened for participation in the study. Subjects who meet all applicable entry criteria will be randomized in a 2:1 ratio to receive either BCV or SoC. The day of randomization is defined as Day 1. During randomization, subjects will be stratified based on the following variables: last (non-baseline) screening AdV viremia ($\geq 10,000$ copies/mL vs. $< 10,000$ copies/mL), time from transplant to randomization (≥ 28 days vs. < 28 days), and T cell-depletion methodology (receipt of alemtuzumab or ex vivo depletion vs. receipt of anti-thymocyte globulin [ATG]). Subjects randomized to receive BCV will be treated until AdV deoxyribonucleic acid (DNA) is confirmed to be undetectable in plasma, up to a maximum of 16 weeks post-randomization. Subjects randomized to the SoC arm will be managed according to local or institutional practice guidelines for the treatment of AdV infection. All subjects, regardless of treatment assignment, will be followed in the study for a total of 36 weeks post-randomization. Subjects will be assessed on a weekly basis through Week 16, with additional assessments performed at Weeks 24 and 36 post-randomization. The data collected through Week 16 will comprise the primary data set for the study; hence, the primary database will be locked and analyzed following capture of data for all subjects through Week 16. In addition, all subjects (both BCV and SoC recipients) will be encouraged to enroll in the BCV Registry (Study CMX001-333) to assess the longer-term impact of exposure to BCV.

Number of Subjects (Planned):

The study will target the enrollment of a total of approximately 141 subjects, with 94 subjects randomized to the BCV arm and 47 subjects randomized to the SoC arm.

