Pediatric subjects have responded to BCV therapy. Study CMX001-304 enrolled 201 subjects (130 pediatric, 71 adult) with disseminated AdV disease or with asymptomatic viremia or localized AdV infection who were at risk for progression to disseminated AdV disease. Subjects were treated with BCV for 12 weeks. In this study, pediatric subjects had improved clinical outcomes compared with adult subjects (all-cause mortality at Week 36 was 39% in pediatric subjects vs. 63% in adults). Key differences between these two groups at baseline suggest that the adults who enrolled in this trial had poorer prognoses than the children (e.g., indication for transplantation, frequency of T cell depletion). Additionally, the time from transplant to BCV initiation was longer for adults (median 94 days) than pediatric subjects (median 53 days), which may reflect earlier diagnosis in the setting of screening protocols that are common at pediatric transplant centers. Pediatric subjects tolerated BCV better than adults and had longer median duration of BCV therapy (78 days vs. 38 days in adults).

Because pediatric recipients of T cell-depleted allogeneic HCT are at very high risk for AdV infection and progression to serious disease, they are among the most in need of new treatment options, and have demonstrated reasonable tolerability and responses with BCV-based therapy. Accordingly, this study will focus enrollment on this population most likely to benefit from treatment with BCV.

Subjects to be excluded are those with baseline comorbidities AdV who are unlikely to survive to Week 4, such as subjects with renal failure or a need for renal replacement therapy, those with pre-existing coagulopathy, sepsis requiring vasopressors, or the need for ventilator support.

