12.1. Determination of Sample Size

A total of approximately 141 subjects will be enrolled into this study. Sample size calculations were based on the primary endpoint, i.e., AAUC through Week 16. Assuming the observed standard deviation of 1.03 log₁₀ copies/mL in AAUC at Week 16 from a comparable subset of SoC subjects, the study has > 90% power with the currently planned sample size to demonstrate superiority of BCV vs. SoC, given that the true difference in means is > 0.6 log₁₀ copies/mL (i.e., an effect size of ~ 0.58). In addition, the overall mortality at Week 16 non-inferiority comparison will have > 80% power in the event that the expected mortality for SoC is 20% to 30% and there is a true mortality advantage of 6% to 9% in favor of BCV ([Feghoul 2015](#), [Hiwarkar 2017](#), [Mynarek 2014](#)).

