- Multiple imputation, where the missing part of the trajectory is imputed based on a model ([Rubin 1978](#)). This imputation is repeated to create multiple simulated data sets (e.g., 5-times the number of deaths plus drop-outs). Each of these simulated data sets is analyzed independently and the results from these analyses are pooled to yield a final inference.
- Undetectable imputation, where the missing part of the trajectory is imputed as undetectable.

In addition to the above, three other supportive analyses are proposed to directly account for subjects who die prior to Week 16:

- Baseline imputation, where the missing part of the trajectory for deaths only is imputed at the baseline value for the subject.
- Analysis of time below the detection limit, whereby subjects who die are considered to be above the detection limit after death. This approach will be repeated using time below 1000 copies/mL, which is a clinically-meaningful level of viremia often signaling viral control vs. need to address in clinical practice.
- Generalized pairwise comparisons of prioritized outcomes ([Buyse 2010](#)). In this approach, all BCV subjects are compared with all SoC subjects in the same stratum. Comparisons will be made based on the following hierarchy:
 - Alive or dead at Week 16
 - If both die before Week 16, compare time to death
 - If both are alive at Week 16, compare AAUC

Each comparison yields a favorable, unfavorable, or neutral result. The “proportion in favor of treatment” (Δ) is the net difference between the number of favorable pairs and the number of unfavorable pairs divided by the total number of pairs. The null hypothesis $H_0: \Delta=0$ is tested using a randomization test.

Another important factor that may influence the primary inference is the imputation of undetectable and BLQ AdV viremia values, with additional sensitivity analyses conducted in order to assess the potential impact of this imputation:

- Impute all undetectable/BLQ values at 1 copy/mL (i.e., 0 log₁₀ c/mL)
- Impute all undetectable/BLQ values at 189 copies/mL
- Impute all values < 1000 copies/mL at 1 copy/mL

In addition, a supportive analysis of overall mortality (adjusting for advanced baseline disease, [Matthes-Martin 2008](#)) will examine the non-inferiority of BCV treatment to SoC. No negative impact on mortality will be concluded if the upper bound of the one-sided 95% confidence

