interval (CI) for the absolute difference between BCV mortality and SoC mortality is $< 10\%$. The proposed sample size will have $> 80\%$ power to demonstrate this conclusion, assuming SoC mortality in the expected range of 20% to 30% and a risk difference of 6% to 9% in favor of BCV (Feghoul 2015, Hiwarkar 2017, Mynarek 2014). In the event this supportive analysis concludes non-inferiority and the primary endpoint is met, superiority for overall mortality at Week 16 will be tested at alpha 0.05. Non-relapse mortality will be assessed in a similar fashion.

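### The supportive pairwise analysis weights each stratum by about the square of its size, which costs power to a degree that depends on stratum sizes the documents do not give

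*Combined protocol and SAP*

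**What the plan says.** Section 12.4.1 lists three supportive analyses that deal directly with deaths before Week 16. The last is a generalized pairwise comparison in which "all BCV subjects are compared with all SoC subjects in the same stratum". Each pair is settled first on vital status at Week 16, then on time to death if both died, then on AAUC if both survived. The summary measure Delta "is the net difference between the number of favorable pairs and the number of unfavorable pairs divided by the total number of pairs". The hypothesis Delta = 0 is tested by a randomization test.

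No stratum weight is named, and the section does not define the strata for this analysis. Section 8.8 lists three two-level randomization factors: screening viremia at 10,000 copies/mL, time from transplant at 28 days, and T cell-depletion method. The documents give neither expected stratum sizes nor a power figure for this analysis.

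**The concern.** Because pairs exist only within stratum and all of them are then pooled, a stratum contributes in proportion to its number of pairs. Doubling a stratum's size quadruples its influence. A child in a large stratum therefore counts for more than a child in a small one, and the estimate is noisier than the same data allow.

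This matters because the primary analysis truncates follow-up at death, and Section 12.4.1 expects about 16% to 24% of subjects to die by Week 16. Of the analyses that address this, the pairwise comparison is the only one that ranks every death below every survivor. Avoidable noise here makes it a weaker check on whether deaths undermine the AAUC result.

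**Working it through.** **Inputs.** The Synopsis plans 141 subjects, "with 94 subjects randomized to the BCV arm and 47 subjects randomized to the SoC arm". Section 12.1 bases power on "Assuming the observed standard deviation of 1.03" log10 copies/mL, "given that the true difference in means is > 0.6". Section 12.4.1 expects SoC mortality of 20% to 30% and a BCV advantage of 6 to 9 points; 20% vs 14% and 30% vs 21% are used here. Two-sided alpha of 0.05 is assumed. The documents give 0.05 for another comparison ("superiority for overall mortality at Week 16 will be tested at alpha 0.05") and none for the pairwise test. Loss to follow-up is taken as zero. The strata are assumed to be the eight cells of the Section 8.8 factors, and the factor splits are assumed.

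**The plan's own figure.** Section 12.1 says "the study has > 90% power with the currently planned sample size to demonstrate superiority of BCV vs. SoC". SE = 1.03 × √(1/94 + 1/47) = 0.184; 0.6/0.184 = 3.26; 3.26 − 1.96 = 1.30; power = 90.3%. The noncentral t gives 89.9%. The stated figure for the primary comparison is reproduced.

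**Weights.** In a stratum of N subjects at 2:1, n1 × n0 = (2N/3)(N/3) = (2/9)N². With no ties, the null variance of the stratum-specific Delta is (N + 1)/(3 n1 n0). The inverse-variance (van Elteren) weight is therefore proportional to n1 n0/(N + 1), which is roughly proportional to N.

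**Variance ratio, pooled to van Elteren.**

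- Pooled: Σ[n1 n0 (N + 1)]/3 ÷ (Σ n1 n0)².
- Van Elteren: 1 ÷ (3 Σ[n1 n0/(N + 1)]).
- Ignoring the +1 and writing p for each cell's share, the ratio is Σp³/(Σp²)².
- 50/50 on all three factors: 0.25³/(0.5³)² = 1.00.
- 60/40 on all three: 0.28³/(0.52³)² = 0.02195/0.01977 = 1.11. With the +1 kept it is 1.10.
- 70/30 on all three: 0.37³/(0.58³)² = 0.05065/0.03807 = 1.33. With the +1 kept it is 1.30.

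**Dominance.** With 70/30 splits the largest cell holds 0.7³ = 34% of subjects (about 48 of 141) but 0.343²/0.58³ = 0.1176/0.1951 = 60% of pairs. With 60/40 splits it holds 0.6³ = 22% of subjects and 0.216²/0.52³ = 0.0467/0.1406 = 33% of pairs.

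**Power.** Each scenario used 5,000 simulated trials of 141 subjects, with random cell sizes, 2:1 allocation within cells, and death ranked worst, then time to death, then AAUC. The range in each row covers the two mortality scenarios. Van Elteren power was about 72% to 77% whatever the mix.

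| Split of the three factors | Power, raw pooling | Points lost vs van Elteren |
|---|---|---|
| 50/50 each | 72% to 74% | about 1 |
| 60/40 each | 67% to 72% | 4.5 to 5 |
| 70/30, 60/40, 50/50 | 66% to 71% | 5.5 to 6 |
| 65/35 each | 64% to 68% | 8 to 9 |
| 80/20, 70/30, 60/40 | 63% to 68% | 8 to 10 |
| 70/30 each | 61% to 66% | 10.5 to 12 |
| 75/25 each | 60% to 64% | 12 to 13 |
| 80/20 each | 59% to 63% | 13 to 14 |

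The simulation error of each power figure is about √(0.7 × 0.3/5,000) = 0.6 points. Sample-size weights perform about as well as van Elteren weights.

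**Further checks.** A true within-stratum permutation test at 70/30 and 20% vs 14% mortality gave 64% against 73%. With no treatment effect, both weightings reject in 5.0% of trials. With a stronger effect or a smaller SD (van Elteren power about 86% to 93%), the loss is about 1 point for equal strata, 3 to 4 at 60/40, 8 to 10 at 70/30 and 10 to 12 at 80/20.

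**The case against.** The strongest reply has four parts.

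**The size rests on assumed splits.** This stands. The only documentary hint covers one factor: Section 4.3.2 reports for an earlier study that "the time from transplant to BCV initiation was longer for adults (median 94 days) than pediatric subjects (median 53 days"). That suggests the under-28-day level is the smaller one. However, that study included disseminated disease, whereas this trial requires first viremia within 21 days and a transplant within 100 days, so randomization may come earlier. Nothing is given on the shares for viremia or depletion method. A reader might infer a firm loss of 5 to 12 points; that range holds only for splits of roughly 60/40 to 70/30 on all three factors.

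**The analysis is supportive.** This also stands. It carries no power claim and no gatekeeping role. Deaths are also addressed by baseline imputation, by time below the detection limit, and by Week 16 mortality as key secondary endpoint. A reader might take the pairwise comparison for the main analysis of deaths, but the documents do not call it that.

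**The pooled Delta is a coherent quantity.** It is the net chance of a better outcome in a randomly drawn within-stratum pair. The proposed weights are most efficient only under a roughly common effect, and their gain shrinks or reverses if the effect is larger in the big strata. This is a fair limit on the fix, but nothing in the plan shows that squared weighting was chosen for that reason.

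**Reweighting does not make the analysis well powered.** True: power stays at about 72% to 77%. The change removes only the avoidable part of the noise.

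**Conclusion.** The point holds as a cheap efficiency improvement. As written, the estimator weights strata by n1 × n0. If the strata are the eight randomization cells, that costs about 1 point of power when they are equal, 4 to 6 under mild imbalance, 8 to 12 when all three factors are moderately skewed, and up to about 14 when they are very uneven. These figures rest on the protocol's AAUC difference, SD and mortality assumptions, a common effect across strata, two-sided alpha of 0.05 and assumed stratum shares. Delta would also describe mainly the largest strata.

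A reader might infer an inflated false-positive rate or a weakness in the primary result. Neither follows: the randomization test keeps its size, the primary ANCOVA does not use these weights, and no stated figure is contradicted.

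**What to change.** In Section 12.4.1, and in the SAP before database lock:

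- State that the strata are the IV/WRS randomization strata.
- Define Delta = Σ(w_s × Delta_s)/Σ(w_s), where Delta_s is the net proportion of favorable pairs in stratum s and w_s = n1s × n0s/(N_s + 1).
- Run the randomization test on this statistic, re-randomizing within those strata.
- Report the raw pooled Delta as a descriptive figure.

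The cost is a sentence or two of text and a small change in code, with no new data and no effect on the error rate. If the strata turn out equal, essentially nothing is lost. The one downside is the reliance on a roughly common effect; showing the stratum-specific values would let readers judge that.

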12.4.2. Secondary Efficacy Endpoints

Continuous secondary efficacy analyses will use the same method used for the primary analysis.

Dichotomous secondary efficacy analyses will be analyzed using a Cochran-Mantel-Haenszel test stratified by each of the stratification factors. Number of failures and failure rates will be presented for each treatment arm. Cochran-Mantel-Haenszel p-values, estimated common odds ratios, and corresponding approximate 95% CIs will be presented for each comparison. The Breslow-Day test will be used to test the homogeneity of the odds ratios. Missing data will be imputed as failure.

Most time-to-event analyses will be performed using Kaplan-Meier methods/plots and Cox models. P-values and hazard ratios along with their 95% CIs will be presented for each treatment comparison. Missing data will be censored, generally at the earlier of the end of study for each subject or the time point for the specific analysis.

Non-relapse mortality will be analyzed with relapse as a competing risk adjusted for baseline strata, with corresponding cumulative incidence plots, Fine-Gray models, and cause-specific and sub-distribution hazard ratios with corresponding 95% CIs.

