4.3.9. PELOD Scoring

Because the pathogenesis of AdV infection is related to lysis of cells in key organs, such as the lungs, liver and gut (and viral load in plasma is thought to reflect the extent of cellular lysis, supported by correlations between peak viral load and mortality; [Heim 2011](#)), capturing decreased viral burden (as viral AAUC) is highly likely to correlate with decreased organ damage. Maximum pediatric logistic organ dysfunction (PELOD) score has been added as a validated surrogate outcome measure for severely-ill pediatric ICU patients ([Leteurtre 2003](#)). It quantifies the degree of dysfunction across several organ systems (neurologic, cardiovascular, renal, respiratory, hematologic, and hepatic) and has been shown to correlate with mortality in pediatric HCT recipients ([Balit 2016](#)), thus offering an opportunity to quantify the effect of BCV vs. SoC in limiting the occurrence of organ dysfunction by AdV infection.

[figure not shown]

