7.2. Subject Exclusion Criteria

Subjects who meet *any* of the following criteria, as applicable, are not eligible to participate in this study. Retesting of exclusionary laboratory results (through the designated central laboratory) is permitted.

[Note: The CTCAE grading scales for diarrhea ([Table 7](#)) and the NIH staging scales for acute GVHD ([Appendix 1](#)) will be used to determine eligibility into this study. Current stool output or volume, as appropriate, should be compared with each subject's pre-transplant stool output or volume (= baseline). Contact the Chimerix Medical Monitor (or designee) for eligibility questions where baseline stool output or volume is unknown or the subject's clinical condition warrants consideration of an alternative baseline measure.]

1. Any CTCAE Grade 4 diarrhea (i.e., life-threatening consequences with urgent intervention indicated) within 7 days prior to Day 1
2. Any CTCAE Grade 2 or 3 diarrhea (i.e., increase of ≥ 4 stools per day over baseline), unless attributed to AdV, within 7 days prior to Day 1
3. NIH Stage 4 acute GVHD of the skin (i.e., generalized erythroderma with bullous formation) within 7 days prior to Day 1
4. NIH Stage 2 or higher acute GVHD of the liver (i.e., bilirubin > 3 mg/dL [SI: > 51 $\mu\text{mol/L}$]) within 7 days prior to Day 1
5. NIH Stage 2 or higher acute GVHD of the gut (i.e., diarrhea > 556 mL/m²/day, or severe abdominal pain with or without ileus) within 7 days prior to Day 1

6. Active malignancy (with the exception of non-melanoma skin cancer), including relapse or progression of the underlying disease for which qualifying transplant was performed
7. Use of vasopressors within 7 days prior to Day 1
8. PT-INR > 2x upper limit of normal reference range (ULN) in the absence of anticoagulation within 7 days prior to Day 1
9. Requirement for mechanical ventilation within 7 days prior to Day 1, or sustained oxygen delivery for > 24 hours within 7 days prior to Day 1, or any oxygen requirement within 48 hours prior to Day 1
10. Estimated creatinine clearance < 30 mL/min or use of renal replacement therapy (e.g., hemodialysis, continuous renal replacement therapy, peritoneal dialysis) within 7 days prior to Day 1
11. ALT > 5x ULN, AST > 5x ULN, or total bilirubin > 3 mg/dL [SI: > 51 µmol/L] within 7 days prior to Day 1

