11.5. PELOD Score

Each subject's PELOD score will be captured at baseline and as a maximum (aggregate) score over the 16-week treatment period; see Appendix 7 for scoring table. For each organ system, the maximum (i.e., worst-case) score over the 16-week treatment period will be used to calculate an aggregate score for the subject.

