12.4. Efficacy Analyses

12.4.1. Primary Efficacy Endpoint

The primary AAUC analysis will utilize all randomized subjects (ITT) in an analysis of covariance (ANCOVA) with all stratification factors included in the model: T cell-depletion method (alemtuzumab or ex vivo cell selection vs. ATG), time from HCT to randomization (< 28 days vs. \geq 28 days), and baseline AdV viremia (continuous \log_{10} copies/mL). These stratification factors have been selected as those that are clearly related to time to immune reconstitution (time from HCT to confirmed AdV viremia > 1000 copies/mL and thus randomization, procedural differences in depth and duration of immune suppression by T cell-depletion method) with resulting expected differences in clearance of viremia, and/or association with mortality (peak viral load). Regarding baseline AdV viremia, subjects will be stratified at the time of randomization according to \geq 10,000 vs. < 10,000 copies/mL; however, this factor will be included in the analysis as a continuous covariate in order to improve power in determining a treatment effect. In the ANCOVA, AdV viremia values that are undetectable will be imputed at 99 copies/mL (i.e., one less than the lower limit of detection of 100 copies/mL) and values that are detected, but not quantifiable (BLQ) will be imputed at 189 copies/mL (i.e., one less than the lower limit of quantification of 190 copies/mL).

Subjects who die or are lost to follow-up (i.e., drop-outs) prior to Week 16 are accounted for inherently in the AAUC approach by truncating their follow-up period, thereby normalizing AUC over time of follow-up (Li 2012). It should be noted that subjects lost to follow-up are anticipated to be zero or negligible, and approximately 16% to 24% of subjects are expected to die by Week 16. Regardless, the primary analysis will be supplemented by a number of planned sensitivity analyses to assess the impact of subjects who die prior to Week 16 and other potential influential elements on the primary inference and to allow for a more comprehensive assessment of efficacy.

The first three approaches are proposed to account for these subjects in a typical missing data framework:

- Jump to reference imputation, where the missing part of the trajectory is imputed from the control group average ([Kenward 2015](#)).

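### Section 12.4.2 analyzes maximum PELOD without the baseline PELOD that the trial collects, which gives up precision but does not cause bias

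*Combined protocol and SAP*

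**What the plan says.** Section 5.3.2 lists maximum PELOD, hospital days and ICU days through Week 16 as other secondary efficacy endpoints. They are neither dichotomous nor time-to-event, so the only analysis rule that reaches them is in Section 12.4.2: "Continuous secondary efficacy analyses will use the same method used for the primary analysis".

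The primary method, in Section 12.4.1, is an "analysis of covariance (ANCOVA) with all stratification factors included in the model". The terms are T cell-depletion method, time from HCT to randomization, and baseline AdV viremia. Viremia is dichotomized for stratification but enters the model as a continuous covariate, for the stated purpose of gaining power. Subjects who die are "accounted for inherently in the AAUC approach by truncating their follow-up period, thereby normalizing AUC over time of follow-up", and "approximately 16% to 24% of subjects are expected to die by Week 16".

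Section 11.5 states that each subject's "PELOD score will be captured at baseline and as a maximum (aggregate) score over the 16-week treatment period", with the worst value for each organ system summed. No analysis section uses the baseline score. Section 4.3.9 explains why the endpoint was added: it is seen as "offering an opportunity to quantify the effect of BCV vs. SoC in limiting the occurrence of organ dysfunction by AdV infection".

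Section 12 defers statistical detail to an SAP and bars SAP amendments after the primary database lock. No separate SAP is in the text supplied, so this point concerns the rule as written in 12.4.2.

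**The concern.** For AAUC, the continuous covariate is the endpoint's own baseline. Carried over unchanged, the model adjusts PELOD for viremia but not for PELOD. A child who enters with organ dysfunction that persists into the treatment period carries those points into the 16-week maximum. That between-subject variation then stays in the residual, and any chance imbalance in baseline scores stays unadjusted. With only 47 subjects in the SoC arm, precision is worth keeping.

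A second, smaller matter is death. A raw day count ends when the subject dies, and a maximum is taken over a shorter period in a subject who dies. The raw arm difference in hospital or ICU days can therefore reflect both length of stay and timing of death, and nothing in 12.4.2 alerts the reader to this.

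**Working it through.** **1. The plan's own figure.** The only stated power is for AAUC: SD 1.03, difference 0.6, 94 vs 47 subjects. SE = 1.03 × √(1/94 + 1/47) = 0.184. Then 0.6/0.184 = 3.26, and 3.26 − 1.96 = 1.30, which gives 90.3% power at two-sided 0.05 (assumed). This agrees with the stated figure of more than 90%. No power is given for PELOD, hospital days or ICU days.

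**2. Can baseline PELOD differ between subjects?** Section 7.2 narrows several components. It excludes, for example, "Use of vasopressors within 7 days prior to Day 1", and also ventilation or oxygen need, creatinine clearance below 30 mL/min, AST above 5x ULN and PT-INR above 2x ULN. It has no exclusion on white cells or platelets. Appendix 7 gives 10 points for white cells below 1.5 x10^9/L, and subjects may be randomized within 28 days of transplant. Appendix 7 also gives 10 points for creatinine of 55 μmol/L or more below one year of age, which the clearance limit need not exclude. Baseline scores can therefore vary.

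**3. Cost and gain of the covariate.** With N subjects and k covariates, the variance of the adjusted difference is proportional to 1/(N − k − 3). Going from k = 3 to k = 4 at N = 141 multiplies it by 135/134 = 1.0075. If the covariate has partial correlation r with the outcome:

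SE ratio = √[(1 − r²) × 1.0075]

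Break-even: r = √(1 − 1/1.0075) ≈ 0.086.

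| Assumed r | SE change |
|---|---|
| 0 | +0.4% |
| 0.1 | −0.1% |
| 0.3 | −4% |
| 0.5 | −13% |
| 0.7 | −28% |

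Simulation of 94 vs 47 subjects, 4,000 trials per value of r, gave +0.3%, 0.0%, −3.9%, −12.8% and −27.4%.

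**4. What r might be.** The documents do not say. As an illustration, let the baseline score be the hematologic 10 points only, present in a fraction b. Let it carry over with probability c and arise newly with probability m. Let each of four other systems reach 10 points with probability q. With h = bc + (1 − b)m:

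r = b(1 − b)(c − m) / √{b(1 − b) × [h(1 − h) + 4q(1 − q)]}

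- Low end (b = 0.1, c = 0.9, m = 0.6, q = 0.25): r = 0.027/(0.3 × 0.99) = 0.09, so the SE change is about 0%.
- High end (b = 0.5, c = 1, m = 0.2, q = 0.05): r = 0.2/(0.5 × 0.656) = 0.61, so the SE change is about −20%.

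**5. Death and raw days.** Section 12.4.1 gives SoC mortality of 20% to 30% and an advantage of 6 to 9 points for BCV. The pairs 20%/14% and 30%/21% imply 47 × 0.20 + 94 × 0.14 = 22.6 deaths (16%) and 47 × 0.30 + 94 × 0.21 = 33.8 deaths (24%), which matches the plan. Let S be survivors' mean stay, equal in both arms, and D the mean day of death, with decedents in hospital until death. Both are assumed. Then:

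raw difference, BCV − SoC = (pSoC − pBCV) × (S − D)

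- With S and D each from 20 to 70 days, this runs from −3.0 to +3.0 days (0.06 × 50) and from −4.5 to +4.5 days (0.09 × 50).
- With simulated SEs (survivor stay gamma with shape 2, capped at 112 days; death day uniform), the largest case is 4.50/5.03 = 0.90 SE.
- In a central case (S = 43, D = 29.5 to 57.5), it is at most 0.26 SE.

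For days alive and out of hospital, the shift from death alone is (pSoC − pBCV) × (112 − S). At S = 43 this is 0.06 × 69 = 4.1 days (0.63 SE) or 0.09 × 69 = 6.2 days (0.90 SE). With equal 20% mortality and a true stay 5 days shorter (43 to 38), raw days give z = 0.84 and the composite gives z = 0.58.

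**The case against.** On PELOD, the strongest reply is that a one-line protocol rule is not the final plan. The SAP may name covariates by endpoint, and the same method might be read as ANCOVA with each endpoint's own baseline. That reading is possible, but the text does not state it, and 12.4.1 introduces viremia as a stratification factor. It is also fair that every correlation above is assumed and that the low end yields no gain. This limits the size of the benefit but not the case for the change, since the worst outcome is a 0.4% larger standard error.

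On hospital and ICU days, a reader might infer that 12.4.2 applies a death rule that fails for counts, and that the endpoints should be replaced or backed by days alive and out of hospital or ICU. The documents do not support this. Normalizing over follow-up is a property of how the AAUC variable is built; what 12.4.2 carries over is most naturally the ANCOVA. A raw count is complete at death, and Section 10.3 uses such counts for resource utilization. The size and sign of the death effect are not established. The composite would not cure the difficulty: in the central case it carries more mortality than raw days do, and it is less sensitive to a true difference in stay. What stands is a caution about interpretation.

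**Conclusion.** The PELOD point holds as a matter of precision. A reader might infer that leaving out baseline PELOD biases the comparison; in a randomized trial it does not. The cost of adding it is fixed at about 0.4% of the standard error. The gain begins at a partial correlation of about 0.09 and reaches 4%, 13% and 28% at assumed values of 0.3, 0.5 and 0.7.

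For day counts, and equally for maximum PELOD, only a descriptive note about death is warranted. The day-count figures rest on assumed lengths of stay and death timing, and no ICU calculation was made.

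Severity is low. These endpoints sit outside the only stated testing sequence, in which, after the primary endpoint and mortality non-inferiority are met, "superiority for overall mortality at Week 16 will be tested at alpha 0.05". It is a free improvement, and an SAP that already names the covariate would settle it.

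**What to change.** Add to 12.4.2 or the SAP, before the Week 16 database lock:

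> Maximum PELOD through Week 16 will be analyzed with the primary ANCOVA plus baseline PELOD as a covariate.

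Keep hospital and ICU days as listed, without the alive-and-out-of-hospital or out-of-ICU composites. At most, add a descriptive summary of these days by arm and by vital status at Week 16. Label it as a non-randomized breakdown, because vital status is itself a post-randomization outcome. Add a note that death ends the day counts and shortens the period over which maximum PELOD is taken, so that raw differences are read alongside Week 16 mortality.

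The cost is one degree of freedom in the PELOD model, one sentence, one note and at most one descriptive table. Baseline PELOD, hospitalizations and deaths are already recorded, so no new data are needed and no endpoint changes. After the lock, Section 12 would make the same change post hoc.
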